## **6. Study Design and Methods**

### *Study Population:*

Study participants will be solicited by emails sent to faculty, residents, nurse practitioners, physician assistants, and registered nurses in Emory and CHOA's Department of Emergency Medicine. Providers from other departments providing care in the emergency department may also be recruited.

Students at Emory and Morehouse will be recruited using electronic and paper flyers posted at pre-approved locations on campus as well as through email to the emergency medicine interest groups at both schools.

In addition, members of the medical community outside of Emory will be recruited via the EnChroma website. A link reading "Emory University Seeks Color Blind ER Health Care Providers for Research Study, READ ON" will be on the main company website taking users to a page with the language in the attached document (Recruitment Language – EnChroma).

Volunteer subjects will first participate in the online screening test. Subjects who test positive for CVD or who know themselves to have a prior diagnosis of CVD will then undergo confirmatory color vision testing with the Farnsworth D15 test and HRR, both with and without EnChroma glasses. This will be performed by study personnel using personal equipment, not during or within Emory Clinic

resources. Visual acuity will also be obtained in addition to subject self-report of their ophthalmologic and medical history. They may also supply previously obtained refraction prescription for use in making their EnChroma glasses.

We will not be entering subjects' medical records to obtain health information at any time.

We do not expect to recruit tritan deficiencies, both because they are rare and because the glasses are not expected to be of benefit to this population. Of note, we expect a gender disparity in this study because CVD disproportionately affects males, though we will enroll both CVD males and females.

#### *Study Participant Risk*

The devices proposed for testing from EnChroma meet the FDA criteria for non-significant risk devices. The glasses pose no serious risk to the health, safety, or welfare of a subject, and they are not of substantial importance in diagnosing or treating disease. Healthcare providers are free to remove or discontinue use of these devices while performing patient care if they are hindering patient care in any way, reverting to their usual care. Furthermore, the glasses are currently available to the public without prescription and providers are able to purchase and wear them during patient care without approval. As such, we do not anticipate any substantive risk to patients while these are worn during patient care. We will encourage participants to remove the glasses if they feel their medical care is being hindered in any way. Of note, the indoor Enchroma glasses do diminish total light transmission somewhat (50% visible light transmission) and a key question in this study is whether that has a significant effect on providers' comfort and ability to deliver care without removing the glasses.

There is a risk of breach of confidentiality, albeit low. No personal identifying information will be collected about the patients examined as part of this study. Data will be aggregated before analysis.

Records of any ophthalmologic examinations performed on entry into the study will be maintained by study staff and destroyed at the end of data analysis. Any new pathologic conditions discovered during that examination will be reported to the subjects so that they may seek medical care as needed.

#### **Consent:**

CVD subjects will sign informed consent at the time of optometrist evaluation. They may discontinue participation in the study at any time.

#### **METHODS**

Each participant with CVD (other than medical students) will be provided EnChroma products to use indoors over the course of two weeks in the emergency department, educational settings, and in their personal life. They will be encouraged to wear the glasses for at least 10 hours over 1-2 weeks prior to wearing them in a clinical setting to adjust to their use, and for 10 minutes before beginning patient care as per manufacturer instructions. They will be encouraged to take specific note of clinical scenarios that require the use of color vision (e.g., - rashes, tympanic membrane erythema, stool guaiac

testing, etc.). Placebo glasses will not be provided given that subjects will not be able to be blinded to the difference, and subjects are unlikely to tolerate red tinted glasses which do not provide benefit. The participant will then complete a survey regarding their baseline experience of having CVD, and the participant's reflections on how CVD has affected his/her clinical practice and education in the past, including any "work-arounds" they have employed previously. The survey will also ask them to reflect on the impact of the glasses on patient care as well as a 100mm scale in addition to open ended questions.

Data will be analyzed both quantitatively (improvement on 100mm visual analog scale and any change in patient survey responses) as well as qualitatively, using thematic analysis of open ended survey data within the grounded theory paradigm.

In the event of substantial missing data, data will be imputed using a multiple imputation procedure. The type of procedure and the number of imputed data sets will be determined by the amount of missing data and the pattern of missingness. However, we do not expect significant missing data in this study. No data will be sent to the FDA.

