## 7. Participant Selection

- **Sample Size Calculation.** Given the number of male providers in Emory's department of Emergency Medicine, and the prevalence of CVD in the general populations, the maximum achievable sample size is expected to be approximately 50 participants. A sample size of 50 will provide sufficient power (80%) to detect a within-group standardized difference (Cohen's  $d$ ) of 0.44 between the glasses-on and glasses-off conditions.
- Inclusion/Exclusion Criteria

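### The plan analyses improvement on a 100 mm VAS, but the only VAS it describes is in the survey completed after wearing the glasses

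*Combined protocol and SAP*

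**What the plan says.** Section 6 (METHODS) sets out the wear period and then the survey: "The participant will then complete a survey regarding their baseline experience of having CVD". It continues: "The survey will also ask them to reflect on the impact of the glasses on patient care as well as a 100mm scale". No other provider survey, and no other VAS, appears in the plan. The quantitative analysis is given as "improvement on 100mm visual analog scale and any change in patient survey responses".

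The same section explains that there is no placebo because "subjects will not be able to be blinded to the difference". It encourages participants to "wear the glasses for at least 10 hours over 1-2 weeks prior to wearing them in a clinical setting", and it limits the wear period: "Each participant with CVD (other than medical students) will be provided EnChroma products".

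Section 7 gives 80% power with 50 participants for a within-group Cohen's d of 0.44 "between the glasses-on and glasses-off conditions". It names no outcome, test or alpha. Section 6 (Study Population) does provide a comparison with and without the glasses, but only for the Farnsworth D15 and HRR colour tests.

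**The concern.** Improvement needs something to improve from. As written, the VAS has no glasses-off value recorded before participants have worn the glasses, and questions about baseline experience are asked only in hindsight, in the same form as the reflections on the glasses.

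At stake is part of the aim, not all of it. The hypothesis in Section 5, that the glasses do not obstruct work or harm care, can be answered from post-wear ratings. But Section 5 also says the surveys will give evidence of effectiveness in patient care. For that claim the VAS result would rest wholly on how participants look back after using glasses they know to be active. A baseline missed at the start cannot be recovered later.

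**Working it through.** **Timing of the VAS.** The scale is in the survey that asks about the impact of the glasses. That question cannot be answered before wear, so the survey is a post-wear survey. No earlier administration is described anywhere.

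**What the score could be.** The survey form is not in the documents, so two readings are open.
- A direct rating of how much the glasses helped. This needs no baseline, but it is retrospective and unblinded.
- A rating set against remembered performance without glasses. This is also retrospective and unblinded, and it adds recall error.

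Neither is a prospective glasses-off value.

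**Whether another source fills the gap.**
- D15 and HRR are measured with and without the glasses, but they are colour tests, not ratings of patient care, and the analysis sentence in METHODS does not name them.
- Glasses-off moments during wear are not neutral. Section 6 (Study Participant Risk) says: "We will encourage participants to remove the glasses if they feel their medical care is being hindered in any way". Those moments are therefore selected for the glasses performing badly.
- Any clinical shifts worked during the adaptation time would be glasses-off for an unrelated reason, but no VAS is collected for them.

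**The plan's own figure.** Inputs from Section 7: n = 50, power 80%, d = 0.44, paired. Assumed: paired t-test, two-sided alpha 0.05. Power comes from the noncentral t with n − 1 degrees of freedom and noncentrality d√n.
- n = 50: noncentrality 0.44 × √50 = 3.11, power 86.2%. The difference detectable with 80% power is 0.404.
- The stated 0.44 at 80% power is approached only under unstated assumptions, for example two-sided alpha 0.025 with a normal approximation (0.436), or 43 completers after about 14% loss (43/0.86 = 50).

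The figure is under-specified rather than wrong, and the present point does not depend on it.

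**Whether a pre-wear item fits the planned sample.** If d = 0.44 is in SDs of the within-participant difference:

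| Complete pairs | Power |
|---|---|
| 50 | 86.2% |
| 45 | 82.3% |
| 43 | 80.5% |
| 42 | 79.5% |
| 40 | 77.4% |

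So 50 − 43 = 7 pairs could be lost while keeping 80%.

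If d = 0.44 is instead in SDs of a single rating, it converts as d_z = 0.44/√(2(1 − ρ)), where ρ is the pre-post correlation (assumed):

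| ρ | d_z | Power, 50 pairs |
|---|---|---|
| 0.3 | 0.372 | 73.2% |
| 0.4 | 0.402 | 79.5% |
| 0.5 | 0.440 | 86.2% |
| 0.7 | 0.568 | 97.6% |

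**Precision.** The 95% CI half-width with 50 pairs is t(0.975, 49)/√50 = 0.284 SD of the difference. For an assumed SD of 20 or 30 mm that is 0.284 × 20 = 5.7 mm or 0.284 × 30 = 8.5 mm.

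These figures describe the remedy. They do not measure the bias, for which the documents give no basis.

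**The case against.** The strongest reply is that this is a feasibility study of subjective reflections. Its hypothesis is answered by post-wear ratings, and a direct rating of perceived impact is a natural reading of the survey text. On that reading no baseline is needed and no recall error arises; what remains is unblinded self-report, which the plan acknowledges. The contrast in Section 7 may also refer to D15 and HRR, which are measured prospectively in both conditions. Finally, a pre-wear item leaves expectation bias and change over time in place, and it measures something slightly different from impact on care.

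Much of this stands. The hypothesis is unaffected, the item wording cannot be checked, and Section 7 cannot be tied to the VAS. The benefit in reduced recall error arises only on the recalled-baseline reading. It is also fair that no extra participants are needed only under conditions: on the single-rating scale, power is below 80% at correlations of 0.3 and 0.4, and 50 is described as about the most that can be recruited.

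None of this supplies a VAS baseline. On either reading the plan promises an improvement analysis and describes only a hindsight rating for it.

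**Conclusion.** The concern holds. No prospective glasses-off VAS value is described, so the VAS evidence on effectiveness would be wholly retrospective and unblinded. The scope is limited: feasibility and tolerability conclusions are untouched, and the size of any bias cannot be estimated from the documents. It should be fixed before participants first try the glasses, because the missing value cannot be collected afterwards.

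The remedy fits the planned 50 if d = 0.44 is in SDs of the difference, or if it is in SDs of a single rating and the pre-post correlation is about 0.5 or higher. Both statements assume a two-sided 5% paired t-test and that all 50 enter the wear period. Confidence is medium, because the survey form is not available and the item may turn out to be a direct rating of impact.

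**What to change.** In Section 6, for participants who will enter the wear period:

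- Move the baseline-CVD questions to a pre-wear contact and add one 100 mm VAS item that can be answered without glasses, for example confidence in colour-dependent patient care during recent clinical shifts.
- Write in the order: consent, VAS item, first try of the glasses. This must precede any testing with the glasses on. The plan does not say that colour testing and consent happen at one visit (Section 6, Study Population and Consent; Section 8), so the order needs stating.
- Repeat the item after wear, worded to refer to clinical shifts on which the glasses were worn, so that adaptation time outside clinical work is not rated.
- Analyse post minus pre within participant, with a 95% CI, and report it as an uncontrolled before-after difference.
- Keep the rating of the glasses' impact as a descriptive post-wear item.

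Two small wording changes belong alongside. Name the outcome behind d = 0.44 in Section 7, and if it is D15 or HRR, add that outcome to the analysis sentence. Describe patient-survey responses without calling them a change unless a comparator is collected.

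The cost is a few minutes per participant at a contact that already takes place. The change removes reliance on a recalled baseline. It does not remove expectation bias or change over time. Because the glasses may be taken off within a shift, the result is not a pure contrast of glasses on with glasses off.

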## **5. Study Aims and Outcomes:**

**Aim:** Evaluate the feasibility of using EnChroma glasses in a patient care environment, as well as subjective reflections on the effects of the product on patient care. CVD providers will wear the glasses for 2 weeks. Providers and patients will be surveyed on the comfort of the product, any subjective influence on color vision overall, specific examples of improvements or hindrances to patient care, and overall impression providing evidence for safety and effectiveness of the product in the patient care setting.

**Hypothesis:** CVD providers will consider EnChroma products to be unobstructive to their daily work and without adverse effect on patient care.

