### Exclusion Criteria

- Age>65
- Chronic eye conditions limiting color vision including:
  - Achromatopsia
  - Cataracts
  - Glaucoma
  - Legal Blindness
  - Macular Degeneration
  - Retinitis Pigmentosa

- Subject Recruitment Plan
  - Faculty, Residents, and Nurses in the Department of Emergency Medicine will be recruited using email to listserves as well as announcements at department and faculty meetings.
  - Students will be recruited through flyers posted on campus and through emails to the EM Interest Group.

- CVD subjects will receive EnChroma products to use for the duration of the study and may keep them at the end. EnChroma will be providing all products necessary for the purposes of the study.
- Screening for eligibility
  - Screening will be self-guided by subjects taking an online color vision test at home on the internet (publicly accessible site). They will share those results with the study investigators prior to enrollment.
- Subject withdrawal
  - Subjects who choose to withdraw will be permitted to keep any EnChroma products which have been provided to them.

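### The plan does not provide for surveying providers who withdraw early or recording why, so if hindrance drives withdrawal the provider result is biased toward unobstructive

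*Combined protocol and SAP*

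**What the plan says.** The hypothesis (section 5) is that "CVD providers will consider EnChroma products to be unobstructive to their daily work and without adverse effect on patient care". Study Participant Risk (section 6) adds, as a key question, whether the reduced light transmission affects providers' comfort and their ability to give care with the glasses on.

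Two ways of stopping are described separately. On stopping use, Study Participant Risk says: "We will encourage participants to remove the glasses if they feel their medical care is being hindered in any way". On leaving the study, the Consent paragraph says: "They may discontinue participation in the study at any time".

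METHODS describes one provider survey, after the two-week wear period. It collects both the baseline experience of color vision deficiency and the impact of the glasses, including a 100mm scale. No interim or exit survey is mentioned.

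The whole of the Subject withdrawal item (section 7) is: "Subjects who choose to withdraw will be permitted to keep any EnChroma products which have been provided to them".

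On missing data, METHODS says: "In the event of substantial missing data, data will be imputed using a multiple imputation procedure". Which method is used, and how many times values are imputed, is left to depend on how much is missing and in what pattern. The authors expect little missing data. No threshold for substantial and no sensitivity analysis is given.

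**The concern.** In this study, leaving because the glasses get in the way is close to a direct answer to the hypothesis. As written, the plan has no means of capturing that answer. A provider who withdraws for that reason cannot be told apart from one who did not return the form.

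The statistical remedy named in the plan does not close the gap. Standard multiple imputation relies on the observed data to explain why values are missing. What is known about a non-responder at entry is D15 and HRR results with and without glasses, visual acuity, and self-reported history. None of these records comfort or hindrance. The baseline-experience questions sit in the same post-wear survey, so a non-responder lacks those as well. Imputed answers would then largely repeat the opinions of those who stayed.

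At stake is the study's main message: it could report that the glasses are unobstructive partly because those who disagreed had left.

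**Working it through.** **1. The plan's own figure.** Section 7 states: "A sample size of 50 will provide sufficient power (80%) to detect a within-group standardized difference". The value it gives for this difference, glasses on against glasses off, is Cohen's d = 0.44. Alpha, sidedness, test and attrition are not stated. With an assumed paired t-test at two-sided 0.05:
- 80% power for d = 0.44 needs N = 43; N = 50 gives 86.2%.
- 45 responders (10% missing) give 82.3%; 40 (20% missing) give 77.4%.
- The stated 80% is therefore not reproduced exactly. It would fit an unstated 14% attrition allowance (43/0.86 = 50), among other unstated choices.

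N = 50 is not shown to be wrong, and nothing below depends on it. Moderate loss costs little power under these assumptions; the problem is bias.

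**2. Bias in a proportion.** Let w be the share of participants missing and p the favourable share among responders. Assume that every non-responder was hindered. The completers-only result is p, and imputation without an informative predictor gives about p. The true value is (1 − w)p, so the overstatement is w × p. With p = 0.90 (assumed):

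| w (assumed) | Reported | True | Overstatement |
|---|---|---|---|
| 5% | 90% | 85.5% | 4.5 points |
| 10% | 90% | 81% | 9 points |
| 20% | 90% | 72% | 18 points |
| 30% | 90% | 63% | 27 points |

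**3. Bias on the 100mm scale.** Bias = share missing × gap between the mean ratings of responders and non-responders. For assumed gaps of 10 to 40 mm:
- 10% missing: 1 to 4 mm
- 20% missing: 2 to 8 mm
- 30% missing: 3 to 12 mm

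**4. Simulation.** Settings were n = 50, normal outcome, 20 imputations and 400 runs per scenario. The least favourable 10%, 20% or 30% of providers were treated as hindered. Bias is in SD of the outcome.

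| Scenario | 10% | 20% | 30% |
|---|---|---|---|
| No hindered provider answers, completers only | 0.19 | 0.34 | 0.49 |
| No hindered provider answers, imputation without a predictor | 0.19 | 0.34 | 0.49 |
| No hindered provider answers, imputation with an entry predictor correlated 0.5 with the outcome | 0.15 | 0.29 | 0.42 |
| Half of the hindered providers answer, imputation without a predictor | 0.09 | 0.15 | 0.20 |
| All hindered providers answer | 0.00 | 0.00 | 0.00 |

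Imputation carries the bias over from the responders and does not create it. A fairly good entry predictor removes only a small part. Collecting the answers removes all of it.

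**The case against.** The strongest reply is that stopping the glasses is not the same as leaving the study. A reader might infer that every provider who takes the glasses off is lost to the survey. The documents do not support that. Removal with a return to usual care is provided for within the study, leaving is a separate right, and METHODS does not restrict the survey to those still wearing the glasses. Section 5 asks for examples of hindrance. Because removal is free, hindrance alone is also a weak reason to withdraw. All of this stands, and it narrows the point to those who withdraw, plus a need to say that those who only stop use are still surveyed.

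A reader might also infer that the imputation rule itself produces the bias, or that the plan commits to filling gaps from completers. Neither follows. The rule applies only to substantial missing data, its type is left open, and completers-only results are biased almost equally.

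Three smaller points also stand:
- Patient surveys are planned. Their timing and any link to a provider are not described, so they cannot be ruled out as a source for imputation, nor relied on.
- Participants are encouraged to acclimatise over 1-2 weeks before clinical wear, so a very early leaver may never have used the glasses in patient care. This is why the stop date matters.
- The plan defines no yes/no criterion for unobstructive, so the proportions above are illustrations and not a planned endpoint.

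Against the expectation of little missing data, the protocol notes that response to the glasses varies between individuals. It also argues that subjects would be unlikely to tolerate tinted glasses that give no benefit. Some hindrance-related loss is therefore plausible on its own reasoning.

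**Conclusion.** The gap is real and should be closed. With one survey after wear, a free right to leave and no collection at withdrawal, loss related to hindrance would tilt the provider result toward unobstructive. Neither completers-only analysis nor standard imputation would correct it. The cause is uncollected data from those who withdraw.

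Confidence is high that the gap exists, and moderate to low on its size. Under the stated assumptions the overstatement is 9 points at 10% missing and 18 points at 20% missing. These are upper-end figures for those missing rates, because they count every non-responder as hindered. The bias shrinks as more hindered providers answer, and it is zero if all do or if withdrawal has nothing to do with the glasses.

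**What to change.** **Section 7, Subject withdrawal.** Ask anyone who stops using the glasses or withdraws to complete the same survey at that point, if willing. Record the date, the reason, and whether they stopped glasses use or left the study. State that those who only stop use remain participants and are surveyed.

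**Section 6, METHODS.**
- Report as a feasibility outcome the number and proportion, among all participants issued glasses, who stopped for discomfort, dimness or hindrance. Do not impute favourable ratings for them.
- Keep multiple imputation for other missing data, and state the model in advance.
- Add a sensitivity analysis that gives non-responders unfavourable values, for example a low value on the 100mm scale.

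The provisions on removing the glasses and on leaving the study stay as they are.

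**Cost.** Protocol wording, an earlier trigger for a survey already planned, and a few recorded items, with no extra staff or procedure. The reported acceptability may be less favourable, and some who withdraw may decline the survey, which is why the sensitivity analysis is still needed.
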